## 6. ENDPOINTS AND COVARIATES

### 6.1. Safety Endpoints

- Adverse events: All undesirable or unintended signs or symptoms that occurred after administration of this drug, regardless of causal relationship
- Adverse drug reactions: Adverse events assessed as causally related to this drug by the physician

- Serious adverse events or serious adverse drug reactions: Adverse events or adverse drug reactions assessed as serious by the physician

- Death after HSCT:

- Time to death after HSCT: Days and weeks from the date of first HSCT after the start of this drug to the date of death
- Event: Death (for any cause)
- Censoring: The patient is confirmed alive at the time of completion or discontinuation of the survey. The endpoint will be censored on the day when patient's survival was last confirmed.

Early death after HSCT is defined as the above event that occurred within 100 days after the first HSCT after the start of this drug. Early death is supposed to be absent if the patient died on 101 days or later, or was confirmed alive at the time of completion/discontinuation of the survey.

- Transplant-related death after HSCT (non-relapse death):

- Time to transplant-related death after HSCT: Days and weeks from the date of first HSCT after the start of this drug to the date of death.
- Event: Death due to non-tumor-related causes, resulting from worsening of the target disease of this drug
- Competing risks: Death due to tumor-related causes, resulting from worsening of the target disease of this drug
- Censoring: The patient is confirmed alive at the time of completion or discontinuation of the survey. The endpoint will be censored on the day when patient's survival was last confirmed.

Early transplant-related death after HSCT (non-relapse death) is defined as the above event that occurred within 100 days after the first HSCT after the start of this drug. Early death is supposed to be absent if the patient died on 101 days or later, or was confirmed alive at the time of completion/discontinuation of the survey.

- Transplant-unrelated death after HSCT (relapse death):

- Time to transplant-unrelated death after HSCT: Days and weeks from the date of first HSCT after the start of this drug to the date of death.
- Event: Death due to tumor-related causes, resulting from worsening of the target disease of this drug
- Competing risks: Death due to non-tumor-related causes, resulting from worsening of the target disease of this drug

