#### 8.2.3.3. Other endpoints

- **Death after HSCT**

To investigate early deaths after HSCT (see Section 6.1 for definition), the following kinds of patient data will be summarized as per Section 8.1.2. The denominator of a proportion is the number of patients included in the 1-step higher itemization level.

- Patients in the SAS who underwent HSCT after the start of this drug and have finished the survey (Patients who are recorded as discontinued in the "Record of continued/discontinued survey [treatment period]" in the case report form or patients for whom "Record of continued/discontinued survey [follow-up period]" in case report form is filled in. The latter means the survey is discontinued and completed for the patient.)
  - Death after HSCT
    - ◊ Death within 100 days post-HSCT
    - ◊ Death after > 100 days post-HSCT
    - ◊ Transplant-related death (non-relapse death)
      - Death within 100 days post-HSCT
      - Death after > 100 days post-HSCT
    - ◊ Transplant-unrelated death (relapse death)
      - Death within 100 days post-HSCT
      - Death after > 100 days post-HSCT

- Survival confirmed at the time of discontinuation of the survey
- **Mortality after HSCT**

Time to death after HSCT, time to transplant-related death after HSCT, and time to transplant-unrelated death after HSCT (see Section 6.1 for definitions) will be analyzed as per Section 8.1.4 (Although the time to death after HSCT does not have any competing risk, the same analysis with competing risks will be performed for the variable). Those who included in the analysis are patients in the SAS who underwent HSCT after the start of this drug and finished the survey (Patients who are recorded as discontinued in the "Record of continued/discontinued survey [treatment period]" in the case report form or patients for whom "Record of continued/discontinued survey [follow-up period]" in case report form is filled in. The latter means the survey is discontinued and completed for the patient.). The cumulative incidence will be estimated at Week 4, Week 8, Week 12, Day 100, Week 24, Week 36, Week 48, Week 52, Week 78, and Week 104.

- **Exploration of factors associated with early death after HSCT (subgroup analyses)**

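### SAP 6.1 defines non-relapse death after transplant as a non-tumor death caused by worsening of the leukemia, a category that is empty as written

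*SAP*

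**What the plan says.** SAP 6.1 sets up two cause-specific endpoints after the first HSCT that follows the start of the drug.

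- **Transplant-related death, labelled non-relapse death.** The event is given as "Death due to non-tumor-related causes, resulting from worsening of the target disease of this drug". For the competing risk, the SAP changes only the cause and keeps the rest of the phrase: "Death due to tumor-related causes, resulting from worsening of the target disease of this drug".
- **Transplant-unrelated death, labelled relapse death.** The same two definitions swap roles. The tumor-related one is the event, and the non-tumor one is the competing risk.

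Both endpoints are censored only for patients known to be alive when the survey ended for them, at the date survival was last confirmed. Each has an early version covering the first 100 days.

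SAP 8.2.3.3 uses these definitions in three places: a table of deaths by cause, split at Day 100; cumulative incidence curves with competing risks; and a subgroup search for factors associated with early transplant-related death. It refers back to 6.1 for the definitions and gives none of its own. Protocol 8.8.12 collects a reason for death but has no rule that maps it to one cause or the other.

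**The concern.** The target disease is relapsed or refractory CD22-positive ALL (Protocol 8.2; SAP 5.2). A death that results from worsening of that disease is a tumor-related death. The non-tumor category therefore asks for two things that exclude each other, under a label that says non-relapse.

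The category carries weight. Fatal VOD/SOS, or a fatal infection in remission, would naturally be counted there. If the text is followed literally, such deaths have no status in either competing-risk analysis. If it is not followed, whoever codes the deaths has to supply a definition that the SAP does not contain.

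**Working it through.** This is a check of wording and logic. The plan's only design calculation, 80.4% power for a VOD/SOS risk factor with 176 patients, has no bearing on it.

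**Step 1. The four definitions side by side.**

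| Endpoint | Role | Cause named | Qualifier attached | Coherent? |
|---|---|---|---|---|
| Transplant-related | Event | Non-tumor | Worsening of target disease | No |
| Transplant-related | Competing risk | Tumor | Worsening of target disease | Yes |
| Transplant-unrelated | Event | Tumor | Worsening of target disease | Yes |
| Transplant-unrelated | Competing risk | Non-tumor | Worsening of target disease | No |

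One definition is faulty and it is used twice. The tumor-related definition is sound in both of its uses.

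**Step 2. Follow one patient through the literal text.** Take a recipient who dies on day 40 after HSCT of a non-leukemic cause while in remission.

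- Event for transplant-related death? No, because the death did not result from worsening of the leukemia.
- Competing event for that endpoint? No, because the cause is not tumor-related.
- Event or competing event for transplant-unrelated death? No, for the same two reasons.
- Censored? No, because the patient is not known to be alive.
- In the early (100-day) version, counted as absent? No. Absence requires death on day 101 or later, or being known alive.

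The patient has no status in any of these analyses.

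**Step 3. What this does to the curves.** Let F(t) be the cumulative incidence of all-cause death after HSCT, and let T(t) and N(t) be the tumor and non-tumor cumulative incidences. If every death has exactly one cause, T(t) + N(t) = F(t). With the literal text N(t) = 0, so the sum is T(t), which falls short of F(t) as soon as one non-leukemic death occurs. If a programmer then censored such deaths at the date of death, the relapse-death estimate would become one minus Kaplan-Meier. That is never below the proper cumulative incidence, and avoiding it is the reason for a competing-risk method.

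**Step 4. Is it repaired elsewhere?** SAP 8.2.3.3 points back to 6.1. SAP 7 imputes dates of death but does not deal with cause. Protocol 8.8.12 collects the reason only. The labels in 6.1 and 8.2.3.3 show the intent but do not replace the definition.

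**Step 5. What depends on it.**

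- *Affected:* the transplant-related cumulative incidence, through its event; the transplant-unrelated cumulative incidence, through its competing risk; the cause-specific Day-100 rows, where the transplant-related counts are hit directly and the two causes no longer sum to total deaths; and the risk-factor analysis of early transplant-related death.
- *Not affected:* all-cause death after HSCT and its Day-100 split, the risk-factor analysis of all-cause early death, overall survival, and the VOD/SOS analyses.

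**The case against.** The strongest reply is that the intent is plain. Tumor-related and non-tumor-related are mutually exclusive terms, the labels point the same way, and SAP 8.2.3.3 lists the two causes as the branches of death after HSCT. The text reads like a negation misplaced in drafting or translation, and hardly any analyst would report zero deaths under a non-relapse heading. This stands, and it limits the practical harm. A reader might infer that the rule cannot separate the two causes at all, or that the competing risk of the transplant-related endpoint is also contradictory. The documents support neither inference. The shared qualifier adds nothing to the split, but it does not remove it, and the tumor-related definition is sound.

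The second reply concerns importance. A reader might infer that the stated objective on risk factors for early death in HSCT recipients (Protocol 7.2; SAP 2.2) is compromised. It is not. SAP 6.1 defines early death after HSCT as death from any cause within 100 days, and the main factor search in 8.2.3.3 uses that endpoint. Early transplant-related death is added in one sentence as a further analysis. SAP 4.1 also makes all testing exploratory. This stands too.

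Neither reply makes the written definition correct. It remains the only definition the cause-specific analyses have.

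**Conclusion.** The point holds as a narrow error in an operative definition. The non-tumor category in SAP 6.1 contradicts itself and its label in both places where it is used, and nothing else in the documents corrects it. It should be corrected because the cause-specific results are reported under it, but it does not threaten the all-cause findings.

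No numerical size can be derived. The documents do not give the number of HSCT recipients, the number of deaths or the mix of causes. It is tempting to assume such counts, suppose a share of deaths with mixed cause, and quote the resulting swing in non-relapse mortality. That would measure how hard it is to attribute deaths such as infection during active leukemia, a difficulty that remains under perfectly worded definitions. It would not measure this error.

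The conclusion rests on one reading: that the target disease is the leukemia under treatment, as Protocol 8.2 and SAP 5.2 indicate. The case report form is not among the documents. It may contain cause-of-death categories, but the SAP does not refer to any for this purpose.

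**What to change.** In SAP 6.1, make the following changes.

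1. Replace the non-tumor definition in both places (event for transplant-related death, competing risk for transplant-unrelated death) with: *death from any cause other than relapse or worsening of the target disease*.
2. Keep the tumor-related definition as death due to worsening of the target disease, and note that relapse counts as worsening, so that the two categories are exact complements.
3. State that deaths are classified by the reason for death recorded under Protocol 8.8.12 and that every death after HSCT falls in exactly one category. Say which category takes a death whose reason is missing or unknown, because otherwise the partition is incomplete.

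A simple programming check follows: the two cause-specific counts, overall and by Day 100, must sum to all deaths after HSCT.

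The cost is a short SAP revision with no new data. A further rule assigning any death during documented relapse to relapse death is not part of this fix. Best response is recorded only up to HSCT or subsequent therapy (Protocol 8.8.11.1), and the follow-up phase assesses VOD/SOS and survival (Protocol 8.7), so post-transplant relapse is not a scheduled variable.

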#### 6.2. Effectiveness Endpoints

- Hematologic response. This is assessed as one of the following categories based on the best overall hematologic response: CR, CRi, progressive disease (PD), relapse, indeterminate, other, assessment not performed. "Other" corresponds to the cases where the clinical assessment of hematologic response was performed but the result did not fall into any of the categories described in the case report form, while "assessment not performed" corresponds to the cases where the clinical assessment was not performed.
- MRD. This is assessed as one of the following categories based on the MRD status: negativity achieved, negativity not achieved, unknown, test not performed.
- Overall survival:
  - Overall survival: Defined as the months from the start of this drug to all-cause death.
  - Event: Death
  - Censoring: The patient is confirmed alive at the time of completion or discontinuation of the survey. The endpoint will be censored on the day when patient's survival was last confirmed.
- Overall survival after the final dose of this drug in patients who underwent HSCT:
  - Overall survival: Defined as the months from the date of final dose of this drug to all-cause death.
  - Event: Death
  - Censoring: The patient is confirmed alive at the time of completion or discontinuation of the survey. The endpoint will be censored on the day when patient's survival was last confirmed.

#### 6.3. Other Endpoints

- Duration of follow-up after the start of this drug: Period from the start date of this drug to the end date of this survey
- Duration of follow-up after HSCT: Period from the date of the first HSCT after the start of this drug to the end date of this survey

#### 6.4. Covariates

Potential risk factors identified from available data including those from clinical studies conducted to date that are associated with development of liver disorders including VOD/SOS as safety specification include:

- Past history of hepatitis or hepatic disease

- Presence/absence of hepatic impairment
- Peripheral blast count immediately before the start of this drug
- ECOG PS before the start of this drug
- Salvage line of the induction treatment with this drug
- Number of treatment cycles of this drug
- HSCT status (performed or not performed)
- Peripheral blast count before conditioning for HSCT

Potential risk factors associated with the occurrence of safety specification events of VOD/SOS include:

- Age
- Past history of hepatitis or hepatic disease
- Platelet count immediately before the start of this drug
- Salvage line of the induction treatment with this drug
- Number of treatment cycles of this drug
- HSCT status (performed or not performed)
- Conditioning with alkylating agents or busulfan
- Total bilirubin, AST, and ALT levels before conditioning for HSCT

Potential prognostic factors associated with achieving hematologic remission include:

- Age
- ALL Status (relapsed or refractory)
- Chromosome karyotype
- Hemoglobin, platelet count, peripheral blast count, and myeloblast count immediately before the start of this drug
- Salvage line of the induction treatment with this drug
- HSCT status (performed or not performed)

Potential prognostic factors associated with overall survival include:

- Age
- ALL Status (relapsed or refractory)
- Chromosome karyotype
- Hemoglobin, platelet count, peripheral blast count, and myeloblast count immediately before the start of this drug
- Salvage line of the induction treatment with this drug
- HSCT status (performed or not performed)
- Hematologic response, MRD

## 7. HANDLING OF MISSING VALUES

The last observation date is defined as the latest full date among the following:

- Date of administration/discontinuation of this drug

- Date of onset/outcome of adverse event
- Date of assessment of hematologic response
- Date of MRD, laboratory tests, or ECG
- Date of ECOG PS assessment
- Date of hematopoietic stem cell transplant
- Start date of drug therapy or non-drug therapy for the target disease
- Date of survival assessment
- Date of last confirmed survival

If the date of death is missing or partial, it will be imputed based on the date of the last confirmed survival and the last observation date:

- If the date of death is missing, the date of the last confirmed survival will be used. If it is also missing, the last observation date will be used. If the day or month + day of the last confirmed survival is missing, the last observation date or the following date, whichever comes later, will be used.
  - If the day of the date of the last confirmed survival is missing: First day of the month and year when survival was last confirmed.
  - If the month + day of the date of the last confirmed survival are missing: January 1 of the year when survival was last confirmed.
- If the day or month + day of the date of death is missing, the date of the last confirmed survival, the last observation date, or the following date, whichever comes latest, will be used.
  - If the day is missing: First day of the month and year of death.
  - If the month and day are missing: January 1 of the year of death.

If the survival confirmation date is missing or partial, it will be imputed based on the last observation date:

- If the survival confirmation date is missing, the last observation date will be used.
- If the day or month + day of the survival confirmation date is missing, the last observation date or the following date, whichever comes later, will be used:
  - If the day is missing: First day of the month and year of the day of survival confirmation.
  - If the month and day are missing: January 1 of the year of the day of survival confirmation.

If for an adverse event, its seriousness, action made, or outcome is missing, it will be handled as "unknown" when summarizing data.

Cleaning-uncompleted data will be in principle handled as follows.

- Items with missing values: They will be handled as missing (or "unknown" for categorical variables) in both summary and listing.
- Items with inconsistent values: They will be handled as missing in both summary and listing. A list of how data were handled will be prepared separately.

- No signature: Descriptions in the case report form with no signature of contract physician (including cases with only signature of an individual other than contract physician) will be handled as missing in both summary and listing. If, despite the existence of a field for the date of signature, no date or inconsistent date (e.g. a date before the start of treatment or future date) is filled in, the descriptions in the case report form will be regarded as lacking signature.

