8.8.12. Confirmation of Survival

The following information will be entered to assess the overall survival during a period from the start date of BESPONSA treatment to the end date of the observation period:

Result of confirmation of survival at the end of the observation period, date of confirming the survival status if the patient is alive, date of death if the patient died (when the date of death is unknown, the last date of confirming survival), reason for death

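### When the death date is wholly missing, the SAP uses the last confirmed survival date without checking it against later records, so an imputed death can precede evidence that the patient was alive.

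*SAP*

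**What the plan says.** SAP section 7 opens its rule for deaths by saying that a missing or partial date will be imputed from both the last confirmed survival date and the last observation date. It then sets out four situations:

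- Death date missing, last confirmed survival date complete: "If the date of death is missing, the date of the last confirmed survival will be used".
- Death date missing, last confirmed survival date missing too: "If it is also missing, the last observation date will be used".
- Death date missing, last confirmed survival date partial: "If the day or month + day of the last confirmed survival is missing, the last observation date or the following date, whichever comes later", where the following date is the first day of the known month or year.
- Death date partial: "the date of the last confirmed survival, the last observation date, or the following date, whichever comes latest, will be used".

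The reference date is described thus: "The last observation date is defined as the latest full date among the following". The list includes "Date of hematopoietic stem cell transplant" and "Date of MRD, laboratory tests, or ECG", as well as adverse event dates, start dates of other therapy for the disease and the last confirmed survival date itself.

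Protocol section 8.8.12 explains where the survival date comes from. The CRF asks for the date of death or, "when the date of death is unknown, the last date of confirming survival".

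**The concern.** The last confirmed survival date is one of the items from which the last observation date is taken. A complete last confirmed survival date can therefore never be later than the last observation date, but it can be earlier. Only the first branch ignores that possibility, and the SAP gives no reason for the difference.

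One result is perverse: a patient whose last confirmed survival date is complete can be given an earlier death than the same patient with that date partial or blank.

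Risk factors for early death in HSCT patients are a stated objective (Protocol section 7.2). The imputed date feeds the tabulation of deaths at 100 days, the cumulative incidence after HSCT and the subgroup risk ratios (SAP section 8.2.3.3), and also overall survival (SAP section 8.2.4.4).

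**Working it through.** The documents give no figure for this rule, so there is none to reproduce. The sample-size calculation does not depend on it.

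**Inputs.** The branches are those of SAP section 7. Early death is death within 100 days after the first HSCT following the start of the drug. It counts as absent if death is on day 101 or later, or if the patient is confirmed alive when the survey ends (SAP section 6.1). The dates below are illustrations, with day 0 the first HSCT. LCS is the last confirmed survival date and LOD the last observation date.

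**Rules compared, death date wholly missing.**
- SAP, LCS complete: death = LCS.
- Harmonised: death = max(LCS, LOD).

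| LCS | LOD | SAP death date | Harmonised death date | Effect of the SAP rule |
|---|---|---|---|---|
| 80 | 120 | 80, early | 120, not early | moved into the window; 120 − 80 = 40 days lost |
| 80 | 95 | 80, early | 95, early | status unchanged; 15 days lost |
| 110 | 150 | 110, not early | 150, not early | status unchanged; 40 days lost |
| 80 | 80 | 80, early | 80, early | none |
| −10 | 0 (the HSCT) | −10, unclassified | 0, early | negative time to death |
| −10 | 130 | −10, unclassified | 130, not early | negative time to death |

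**The other branches on the first patient.** With LOD on day 120 and LCS blank, the SAP gives day 120. With LCS partial and its first-of-month date on day 70, the SAP gives max(120, 70) = 120. Only the complete LCS gives day 80.

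**When the early-death count rises.** It rises only if LCS lies on days 0 to 100 and some other record lies after day 100. An LCS before the transplant gives a negative time, which is neither within 100 days after HSCT nor on day 101 or later. The SAP does not say how such a value would be handled.

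**Which records can lie after day 100.** After baseline, the schedule in Protocol section 8.8 asks for laboratory tests and ECOG PS only as HSCT pretreatment data. Remission and MRD are assessed only up to HSCT or the next treatment (sections 8.8.11.1 and 8.8.11.2). Adverse events other than VOD/SOS stop at Day 28 post-treatment (sections 8.7 and 8.8.14). What remains is mainly VOD/SOS dates, the start of later therapy and a second HSCT.

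**Size.** With n HSCT recipients in the analysis and k deaths moved across day 100, the early-death proportion changes by k/n. The documents give neither number. Assuming n from 40 to 100:
- k = 0: no change.
- k = 1: 1/40 = 2.5 points to 1/100 = 1.0 point.
- k = 5, taken as an upper value for illustration only: 5/40 = 12.5 points to 5/100 = 5.0 points.

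**The case against.** The strongest reply is that the field, properly completed, prevents the conflict. Section 8.8.12 asks for the last date on which survival was confirmed. A patient who had a transplant or began a new therapy on a later date was alive then, so a correct entry cannot precede that record. The sponsor can query the CRF (Protocol section 8.11.5.2). SAP section 7 also treats inconsistent values as missing in data that have not been fully cleaned, and a last confirmed survival date set to missing would lead to the last observation date.

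Much of this stands, and it is why the number affected is probably small. It does not close the gap. An imputation rule exists for imperfect entries, and the neighbouring branches already guard against this one. The provision on inconsistent values applies in principle only, to data with cleaning incomplete, and it does not say that a survival date earlier than another record counts as inconsistent.

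A reader might go further and infer that the rule inflates early death. The documents do not support that. Inflation needs the date pattern in the first row of the table, few records that could produce it are collected after HSCT, and a survival date before the transplant gives an unclassifiable time, not an extra early death. A reader might also suppose that routine laboratory tests after transplant would supply the later date, but those are not scheduled items. Finally, SAP section 4.1 makes all testing exploratory, so no decision rule turns on one reclassified patient.

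**Conclusion.** The branch for a wholly missing death date is inconsistent with the others in the same section and permits an imputed death before a recorded sign of life. For any patient affected, overall survival is shortened by the gap between the two dates, as is time to death after HSCT. Early-death status changes only for some date patterns, and a death placed before the transplant has no category.

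This is a minor point. The number of affected patients is unknown and may be zero. The 1.0 to 2.5 points per reclassified death rest on an assumed 40 to 100 HSCT recipients and say nothing about how many deaths would be reclassified. Harmonising the rule removes the impossible ordering. It does not remove all bias towards early dates, since the death would still be placed at the last record.

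**What to change.** In SAP section 7, replace the first branch with: *where the date of death is wholly missing, impute the later of the last confirmed survival date and the last observation date*. Keep the existing provisions for a last confirmed survival date that is itself missing or partial. This matches the partial-date branches.

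Report the number of death dates imputed, overall and among HSCT recipients, so that readers can judge whether the rule matters.

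The cost is one SAP sentence, a small change to the derivation program and one reported count. Data collection and sample size are unaffected.
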